9.4 Randomization and Blinding

This is a randomized, open-label treatment study. Patients will be randomized 1:1 to receive SEL-212 or KRYSTEXXA. Randomization preferably should occur 7 days prior to the first dose of study drug (ie, Day -7). The randomization will be stratified for tophus presence (yes/no). Assessments of qualitative endpoints will be conducted on an assessor-blinded basis.

Prior to study drug administration in Treatment Periods 2 through 6, the Investigator will determine a patient's eligibility for treatment with study drug by evaluating the patient's SUA level measured from the blood sample obtained from Day 21 of the most recently completed Treatment Period (SEL-212 cohort) or from the previous 2 measurements (KRYSTEXXA cohort).

Study personnel will endeavor to safeguard the integrity of the qualitative endpoint blind to minimize bias in the study.

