13. STATISTICS

Details of the statistical methods outlined in the protocol for this study, including the hierarchical ordering of the secondary endpoints, will be documented in a Statistical Analysis Plan (SAP) that will be finalized prior to first patient randomized. The SAP may add additional exploratory analyses; modifications to the planned analyses will be identified as such in the SAP.

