13.1 Sample Size Determination

The primary efficacy criterion in this study is defined as the percentage of subjects who achieve and maintain reduction of SUA < 6 mg/dL for at least 80% of the time during Treatment Period 3 and Treatment Period 6.

The percentage of responders according to the above criterion is assumed to be 65% in the SEL-212 arm and 44% in the KRYSTEXXA arm.

Using the Chi-square test for comparison between the SEL-212 arm and the KRYSTEXXA arm, and considering a one-sided alpha=5% and the statistical power of 80%, results in 69 subjects per treatment group. Taking into account that some subjects may be excluded from the modified Intent-to-Treat (mITT) analyses (Section 13.2.4), 75 subjects per treatment group will be randomized. For the sample size estimation, Chi-square test, instead of the Cochran-Mantel-Haenszel test, is used although the randomization will be stratified for tophus presence (yes/no) as there is no valid assumption of the distribution of this stratification variable within the eligible subject population.

Sample size calculations were performed with the software package nQuery Advisor® Sample Size Calculator V. 8.2.1.0.

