The proportion of time that the SUA level is < 6 mg/dL will be computed by taking the ratio between the time during which the SUA level remains < 6 mg/dL (if necessary, using the linear interpolation method) and the entire time interval within Treatment Periods 3 and 6.

Let T_1 be the total time interval in hours for Treatment Period 3 of which W_1 hours is the time interval during which SUA level is < 6 mg/dL. Similarly, for Treatment Period 6, assume T_2 is the total time interval in hours of which W_2 hours is the time interval during which SUA level is < 6 mg/dL. For a subject to be considered a responder, the proportion of time that the SUA level is < 6 mg/dL during Treatment Periods 3 and 6 must be at least 80%. The proportion of time that the SUA level is < 6 mg/dL, i.e., percentage of non-hyperuricemic time, is calculated using the following formula:

$$\text{Proportion} = \frac{W_1 + W_2}{T_1 + T_2} \times 100$$

A logistic regression model controlling for the distribution of baseline characteristics will be performed as supportive analysis.

Summary tables of the percentage of responder (subjects who achieve and maintain reduction of SUA < 6 mg/dL for at least 80% of the time) in each treatment period will be provided by treatment group. Additionally, a summary table with the total time a subject has SUA values < 6 mg/dL will be provided for each treatment period by treatment group.

Summary tables of the actual values and change from baseline for SUA results will be provided for each scheduled sampling time point by treatment group.

Additionally, mean SUA level, reduction in mean SUA and percent reduction in mean SUA from baseline during Treatment Period 3 or Treatment Period 6 will be presented by treatment group.

- Mean SUA level is defined as the area under the SUA time curve (computed using the linear trapezoidal rule during Treatment Periods 3 and 6) divided by the corresponding time interval.
- Reduction in mean SUA is computed by subtracting baseline SUA level from mean SUA during Treatment Period 3 and 6.
- Percent reduction in the mean SUA from baseline is computed as the mean SUA level during Treatment Periods 3 and 6 minus baseline SUA level divided by baseline SUA level multiplied by 100

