The estimator for the comparison between the treatment groups is defined as the difference in the proportion of responders between patients receiving SEL-212 versus those receiving KRYSTEXXA® during Treatment Periods 3 and 6. The statistical testing will be performed confirmatory using the Cochran-Mantel-Haenszel (CMH) test – considering the randomization stratum of tophus presence (yes/no) – with a one-sided type 1 error rate $\alpha = 5\%$. In addition, 90% two-sided confidence intervals for the overall treatment difference between SEL-212 and KRYSTEXXA® treatment groups without stratification will be computed. The analysis of the estimands will be carried out based on the ITT primarily. Supportive analyses will be performed on the mITT and the PP.

A logistic regression model to compare treatment difference controlling for presence of tophus will be performed as supportive analysis.

In addition, a sensitivity analysis will be performed as below for the primary endpoint:

- If a subject withdraws from study treatment before completing period 6 due to stopping rules met for treatment, the subject will be considered as a non-responder for the primary efficacy endpoint.
- If a subject withdraws from the study before completing period 6 or the study terminates prior to a subject completing period 6, the primary efficacy endpoint is based on SUA assessment for period 3 where $T1$ be the total time interval in hours for Treatment Period 3 of which $W1$ hours is the time interval during which SUA level is < 6 mg/dL:

$$\text{Percentage (p)} = \frac{W1}{T1} \times 100$$

Summary tables of the percentage of responders (patients who achieve and maintain reduction of SUA < 6 mg/dL for at least 80% of the time) will be provided by treatment group. Additionally, a summary table with the total time a patient has SUA values < 6 mg/dL will be provided for treatment period 3 and treatment period 6 by treatment group.

Summary tables of the actual values and change from baseline for SUA results will be provided for each scheduled sampling time point by treatment group.

This document is confidential.

Additionally, mean SUA level, reduction in mean SUA and percent reduction in mean SUA from baseline during Treatment Periods 3 and 6, during Treatment 3, and during Treatment Period 6 will be summarized by treatment group respectively and will be compared for treatment difference using ANOVA model with presence of tophus and treatment group as fixed factors

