7.4. Deviation from Analyses Planned in Protocol

7.4.1. Additional analyses

The following analyses are added even though they are not included in the protocol:

- Interim analysis.
- Subgroup analyses on the secondary endpoint by patient's primary efficacy endpoint (responder vs. non-responder).

The following analyses have been added as a result of the impact of Covid-19 on the study which may result in a larger anticipated number of subjects not completing the study and therefore not undergoing the assessments required for the primary efficacy endpoint or the study being stopped prematurely by sponsor decision. This is in line with FDA Guidance on Conduct of Clinical Trials of Medical Products during COVID-19 Pandemic Guidance for Industry, Investigators, and Institutional Review Boards.

- Additional analyses suggested to primary endpoint as sensitivity analyses to determine if the impact that these have on the conclusions of the study and to describe the impact of Covid-19 on the study performance.
- A sensitivity analysis which limited the analysis to results processed in the central laboratory to determine if this resulted in different conclusions to those found from the full analysis to determine consistency in laboratory testing between central and local laboratories.
- Kaplan-Meier analysis of withdrawal from study by treatment arm and presence of tophus to determine if subjects withdraw from the study in different proportions and at different rates within the treatment groups and depending on the presence of tophus.
- Kaplan-Meier analysis of withdrawal from study due to an adverse event by treatment arm and presence of tophus to determine if subjects experience adverse events in different proportions and at different rates within the treatment groups and depending on the presence of tophus.
- Poisson regression with number of gout flares experienced during treatment periods 1-6 as the dependent variable, treatment and the presence of tophus as independent variables and length of follow up as a covariate. The ITT population would be used to conduct this analysis. Similar analysis is done for periods 4-6.

This document is confidential.

8. Safety

The population used for safety analyses will be the Safety Set (SS). Safety will be assessed on the basis of adverse event (AE), clinical laboratory data, ECG parameters, physical examinations, and vital signs.

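### SAP 7.1 limits the supportive logistic model to tophus presence, short of the protocol's baseline-characteristics wording, and SAP 7.4 does not declare it

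*SAP*

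**What the plan says.** Protocol 13.4.1, and the matching paragraph of the synopsis, plan: "A logistic regression model controlling for the distribution of baseline characteristics will be performed as supportive analysis". The characteristics are not itemized. Protocol 13 leaves detail to the SAP, on the condition that "modifications to the planned analyses will be identified as such in the SAP".

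SAP 7.1 carries the model forward as: "A logistic regression model to compare treatment difference controlling for presence of tophus will be performed as supportive analysis". In the same section the confirmatory CMH test is stratified by tophus presence, which Protocol 9.4 gives as the only randomization stratum. For the accompanying 90% interval the wording is "treatment groups without stratification will be computed", so that interval is adjusted for nothing.

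SAP 7.4.1 has one list opening "The following analyses are added even though they are not included in the protocol" (the interim analysis and a responder/non-responder subgroup analysis) and a second list of analyses added because of Covid-19. Neither mentions the logistic model.

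**The concern.** The protocol's plural wording leads a reader to expect a model that brings in baseline information beyond the randomization stratum. The SAP model brings in only the stratum, which the primary test already uses. If the two analyses nearly always agree by construction, their agreement supports the primary result very little.

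The natural omission is baseline SUA. SAP 7.1 substitutes it for missing pre-dose and Day 28 values, so it can enter the endpoint directly. When the curve is drawn from a value a below 6 up to an imputed baseline B above 6, the share of that interval counted as below 6 is (6 - a)/(B - a), which shrinks as B grows. SAP 7.2.2 to 7.2.6 already use the baseline value as a covariate for the questionnaires and joint counts. The SUA analyses do not.

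At stake is the informativeness of one supportive analysis and the traceability of a change from the protocol. The confirmatory conclusion does not depend on it.

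**Working it through.** **1. Does any other planned analysis of the primary endpoint adjust for a further baseline value?**

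| Planned analysis | What it changes | Baseline variables used |
|---|---|---|
| CMH test (SAP 7.1) | primary | tophus |
| 90% interval (SAP 7.1) | estimate | none |
| Logistic model (SAP 7.1) | supportive | tophus |
| mITT and PP repeats (SAP 7.1) | population | none further |
| Non-completer sensitivity analysis (SAP 7.1) | handling of withdrawals | none further |
| Central-laboratory analysis (SAP 7.4.1) | data source | none further |

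The ANOVA on mean SUA in SAP 7.1, a different outcome, also uses only tophus and treatment. The answer is no.

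**2. Planning inputs.** Protocol 13.1 gives 65% and 44% and states: "considering a one-sided alpha=5% and the statistical power of 80%, results in 69 subjects per treatment group". With pooled variance and no continuity correction:

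n = [1.645 x sqrt(2 x 0.545 x 0.455) + 0.842 x sqrt(0.65 x 0.35 + 0.44 x 0.56)]^2 / 0.21^2 = (1.158 + 0.579)^2 / 0.0441 = 68.5, so 69 per arm. The plan's figure is reproduced. Power is 80.3% at 69 per arm and 83.1% at the 75 randomized.

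**3. How close is the tophus-only model to the CMH test?** In stratum k let n_k be the patients, n1_k and n0_k the arm sizes, r_k the responders and a_k the SEL-212 responders.

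- Both the CMH statistic and the score test for treatment in the tophus-only logistic model have numerator sum of (a_k - n1_k r_k / n_k).
- The CMH variance is the sum of n1_k n0_k r_k (n_k - r_k) / [n_k^2 (n_k - 1)]. The score variance has n_k^3 in place of n_k^2 (n_k - 1).
- The standard errors therefore differ only through sqrt(n_k/(n_k - 1)). With expected strata of 60 and 90, or 45 and 105, this lies between sqrt(105/104) = 1.005 and sqrt(45/44) = 1.011.

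This was checked by simulation: 150 patients, 1:1 within stratum, marginal rates 65% and 44%, one-sided 5%, 4,000 trials in each of 12 scenarios. Tophus prevalence was 70% (Protocol 5.4) or an assumed 40%. The tophus log odds ratio (assumed) was 0 or -0.7. A further covariate had an assumed log odds ratio of 0, 0.5 or 1.0 per SD.

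- Tophus-only Wald test against CMH: same decision in 99.5 to 99.8% of trials, correlation of z at least 0.9998, power within 0.5 point.
- Score version against CMH: same decision in 99.0 to 99.6%, z never more than 0.043 apart.

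**4. What does one further covariate add?** Ranges are over the four tophus settings.

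| Assumed log odds ratio per SD (odds ratio) | CMH power | Power with tophus + covariate | Gain, points | Same decision as CMH |
|---|---|---|---|---|
| 0 (1.00) | 82.1-84.8% | 83.1-84.6% | -0.2 to +1.0 | 98.3-98.5% |
| 0.5 (1.65) | 82.1-83.7% | 84.1-85.8% | 1.7 to 2.9 | 94.9-95.5% |
| 1.0 (2.72) | 82.2-85.0% | 88.4-90.0% | 5.0 to 6.6 | 90.5-92.4% |

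The Monte Carlo standard error of a single power is about sqrt(0.83 x 0.17 / 4000) = 0.6 point. Gains are paired within trial and more precise: with 5% discordant decisions, about sqrt(0.05/4000) = 0.35 point.

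Separate runs at assumed odds ratios of 1.5, 2.0 and 2.7 per SD, some with a second unrelated covariate also fitted, gave gains of about 2-3, 3-4 and 5-7 points. With two added covariates, type 1 error was 4.8 to 5.5% and the standardized risk difference had about the same power as the odds-ratio test.

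**The case against.** The strongest reply is that nothing named was dropped. The protocol lists no covariates and delegates detail to the SAP, and tophus presence, assessed at Screening, is itself a baseline characteristic. The SAP could be read as the minimal specification of an open phrase. That reading is possible, but the plural fits poorly with a single variable already balanced by stratification, and a deliberate narrowing should still have been declared.

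Three stronger readings are tempting and should not be drawn.

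- *The model was meant to show that the result is not due to baseline imbalance, and now cannot.* Neither document gives it that purpose; both call it supportive and no more. The trial is randomized, and the type 1 error of the CMH test already allows for chance imbalance.
- *The model is a pure duplicate.* It yields a tophus-adjusted effect estimate, which the unstratified interval does not.
- *Weight must be included because SEL-212 is dosed per kg and KRYSTEXXA at a fixed amount (Protocol 10.1).* That argument concerns a treatment effect varying with weight, an interaction that a linear main effect would not test. No passage says that weight predicts response.

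It is also fair that power is not the purpose of a supportive analysis, and that the gains depend on prognostic strengths found nowhere in the documents. Both points stand, so the power figures serve mainly to show that the change costs nothing.

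**Conclusion.** The point holds as a minor one. The SAP model uses fewer baseline variables than the protocol wording implies, the difference is undeclared in SAP 7.4 despite Protocol 13, and what remains gives nearly the same inference as the CMH test. The near-identity is algebraic and does not depend on the assumed covariate strengths. The power gains do: they are conditional on the assumed odds ratios, on marginal rates of 65% and 44%, and on 75 per arm. They apply to the supportive analysis only.

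**What to change.** Before any primary-endpoint results are seen, including those of the interim analysis in SAP 2.2, amend the SAP as follows.

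- **Model (SAP 7.1):** logistic regression with treatment, tophus presence and baseline SUA as a linear term. Baseline weight is an optional further covariate, to be decided in advance.
- **Baseline rule:** the last pre-infusion value, as in SAP 5.8. The ITT set includes patients never dosed, for whom that definition gives no value, so use their screening value.
- **Estimate:** the standardized risk difference, that is, the mean over all ITT patients of the predicted response probability under SEL-212 minus that under KRYSTEXXA. Give a 90% interval with a named variance method (delta method or influence function). This matches the difference in proportions that SAP 7.1 defines as the estimator.
- **Declaration (SAP 7.4):** list the change from the protocol and the covariates chosen.

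If the sponsor prefers to keep the tophus-only model, the minimum is to list the narrowing and its reason in SAP 7.4.

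The cost is a few sentences of SAP text and modest programming. SUA and weight are already collected at Screening. The CMH test, the one-sided 5% level and the 75 per arm do not change.

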5.6. Protocol Deviations

All protocol deviations related to study inclusion or exclusion criteria, conduct of the trial, patient management, dosing, and sampling procedures or patient assessment will be listed. The list of protocol deviations will be reviewed by the Sponsor, the principal investigator, the study statistician and the study pharmacokineticist and finalized before database lock. Determination of whether the deviation is major or minor, or has impacts on primary efficacy assessment will be based on the biasing impact of the deviation on the safety and efficacy data. Major protocol deviations affecting the primary efficacy assessments include: 1) major protocol deviations that lead to premature study drug discontinuation; 2) major protocol deviations that lead to patients receiving study drug treatment in treatment periods 3 or 6 that they would not otherwise have received (such as incorrect application of the protocol stopping rules that allow a patient to continue dosing despite having met the stopping criteria); and 3) protocol deviations that involve out of window sampling of SUA due to a) visits occurring outside of the protocol visit window for dosing days (where dosing days refer to dosing visits of patients still on study drug who have not previously been withdrawn from study drug) in Treatment period 3 and 6, b) visits occurring outside of the protocol visit

This document is confidential.

window for visits within TP3 or TP6 scheduled 1 week prior to the dosing days, c) visits occurring outside of the protocol visit window for TP6 D21 for patients who have not been withdrawn from study drug and for dosing day TP4D0, or d) visits occurring 35 days or more beyond TP6D0 for the TP6D28 visit for patients who have not been withdrawn from study drug, where the protocol visit window above refers to the current protocol window allowed at the time of analysis. Major protocol deviations affecting the primary efficacy assessments will be reviewed and determined periodically during clinical and medical review of protocol deviations during the study.

Protocol deviations related to Covid-19 will be identified and flagged.

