7.1. Primary Efficacy Endpoint Analysis

The primary efficacy endpoint is defined as:

- Comparison in the percentage of patients on SEL-212 vs. KRYSTEXXA® who achieve and maintain reduction of SUA < 6 mg/dL for at least 80% of the time during Treatment Period 3 and Treatment Period 6

The SUA time curve will be used to estimate the proportion of time that the SUA level is below 6 mg/dL. Based on the serum samples collected during Treatment Periods 3 and 6, an estimate of the time with SUA < 6 mg/dL can be determined by connecting each two neighboring data points with a straight line. SUA values collected at unscheduled visits within period 3 and period 6 will be included for the SUA time curve. If the SUA time curve goes above 6 mg/dL the linear interpolation method will be used to estimate the point in time at which the SUA time curve intercepts the line between the last SUA value < 6 mg/dL and the first value \geq 6 mg/dL.

The proportion of time that the SUA level is < 6 mg/dL will be computed by taking the ratio between the time during which the SUA level remains < 6 mg/dL (if necessary, using the linear interpolation method) and the entire time interval within Treatment Periods 3 and 6. For period 3, entire time interval is between time of day 0 SUV assessment for period 3 and period 4. For Period 6, the entire time interval is between time of day 0 and day 28 assessment.

Let T1 be the total time interval in hours for Treatment Period 3 of which W1 hours is the time interval during which SUA level is < 6 mg/dL. Similarly, for Treatment Period 6, assume T2 is the total time interval in hours of which W2 hours is the time interval during which SUA level is < 6 mg/dL. For a patient to be considered a responder, the proportion of time that the SUA level is < 6 mg/dL during Treatment Periods 3 and 6 must be at least 80%. The proportion of time that the SUA level is < 6 mg/dL, i.e., percentage (p) of non-hyperuricemic time, is calculated using the following formula:

$$\text{Percentage (p)} = \frac{W1 + W2}{T1 + T2} \times 100$$

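### The SAP's one non-completion sensitivity analysis scores study withdrawals outside the stopping rules on Treatment Period 3 alone, whatever the reason, although it was added for Covid-19 losses

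*SAP*

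**What the plan says.** **Primary analysis (SAP 7.1).** Time with SUA below 6 mg/dL is pooled over TP3 and TP6 as (W1 + W2)/(T1 + T2). For a responder, "the proportion of time that the SUA level is < 6 mg/dL during Treatment Periods 3 and 6 must be at least 80" per cent. Anyone who withdraws from the study before completing TP6, or returns to urate-lowering therapy, is a non-responder. A patient who stops study drug but keeps attending is scored on observed data.

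**Sensitivity analysis (SAP 7.1).** It has two bullets:
- Bullet 1: withdrawal from study treatment before the end of TP6 because a stopping rule was met makes the patient a non-responder.
- Bullet 2: "If a subject withdraws from the study before completing period 6 or the study terminates prior to a subject completing period 6", the endpoint becomes W1/T1, that is, TP3 only. No reason for withdrawal is named or excluded.

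The SAP does not say which bullet governs a patient who fits both.

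**Stated purpose (SAP 7.4.1).** The extra analyses were "added as a result of the impact of Covid-19 on the study", because more patients might not finish or the sponsor might stop the study early. The other sensitivity analysis listed there restricts results to the central laboratory and does not address non-completion.

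**Related text.** Protocol 13.4.1 promises sensitivity analyses with different imputation approaches for each estimand and leaves the details to the SAP. SAP 5.6 states: "Protocol deviations related to Covid-19 will be identified and flagged". SAP 5.9 lists eCRF data missing because of Covid-19. Neither provision classifies withdrawals.

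**The concern.** A rule meant for pandemic losses should apply to pandemic losses. Loss of TP6 data because a site closed or the sponsor stopped the study may have little to do with treatment, and falling back on TP3 is then a defensible choice. Leaving after an infusion reaction or another adverse event is different: it may itself be a treatment failure. Bullet 2 treats the two alike.

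It also makes leaving the study score better than staying in it. A patient who stays is judged on TP3 and TP6 together, while one who leaves is judged on TP3 alone.

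This is the only analysis that varies how non-completion is handled. If it agrees with the primary result, the agreement may come partly from crediting treatment-related dropouts. If it disagrees, the reader cannot tell whether Covid-19 or tolerability is the cause.

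**Working it through.** **1. The plan's own figure.** Protocol 13.1: response is "assumed to be 65% in the SEL-212 arm and 44% in the KRYSTEXXA arm"; "considering a one-sided alpha=5% and the statistical power of 80%, results in 69 subjects per treatment group"; "75 subjects per treatment group will be randomized".

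Pooled-variance formula: n = [z(0.95)·√(2·p̄·q̄) + z(0.80)·√(p1q1 + p2q2)]² / (p1 − p2)², with p̄ = 0.545.

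n = [1.645·√0.49595 + 0.842·√0.4739]² / 0.21² ≈ 3.02/0.0441 ≈ 68.5, so 69 per arm. This matches. Power is 80.3% at 69 and 83.1% at 75. The sample size is not in dispute. It supplies the denominator, 75, and the planned difference, 65 − 44 = 21 points.

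**2. One patient, two routes.** Take equal 28-day periods and a patient with 100% control in TP3 who has an adverse event in TP4.
- Stops drug, stays in the study, 0% control in TP6: p = (28 + 0)/(28 + 28) = 50%, non-responder. To respond, the patient would need a TP6 share of at least 2 × 80% − 100% = 60%.
- Leaves the study: p = W1/T1 = 28/28 = 100%, responder under bullet 2. The primary analysis makes this patient a non-responder.

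**3. Is TP3 control of 80% automatic?** No. In the SEL-212 arm a Day 21 SUA above 6.0 mg/dL in TP3 ends dosing, so anyone dosed in TP4 is likely to have good TP3 control, but not certain to. Illustrative curves with low samples after dosing until Day 14:
- Day 21 = 3 and Day 28 = 10 mg/dL: time above 6 is (10 − 6)/(10 − 3) × 7 = 4 days, so control is 24/28 = 85.7%, a responder.
- Day 21 = 5.9 and Day 28 = 8 mg/dL: time above 6 is (8 − 6)/(8 − 5.9) × 7 = 6.67 days, so control is 76.2%, a non-responder.

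**4. Effect on one arm.** Every study withdrawal is a non-responder in the primary analysis, so for these patients bullet 2 can only add responders. Each is worth 1/75 = 1.33 points. Protocol 13.1 gives no dropout rate; it says only that "some subjects may be excluded from the modified Intent-to-Treat (mITT) analyses". As an assumption, let 10% of an arm leave after TP3 with 50-80% of them controlled in TP3. The gain is 10% × 50% = 5 points to 10% × 80% = 8 points. A 5-percentage-point gap between arms in such exits would shift the difference by 2.5 to 4 points.

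**5. Effect on the difference.** The counts below are assumed, at 75 per arm, with an unstratified pooled z-test, one-sided. The starting point is 42/75 against 33/75 with dropouts as non-responders.

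| TP3-controlled dropouts rescored as responders | Difference (points) | p |
|---|---|---|
| None | 12.0 | 0.071 |
| 2 in SEL-212 only | 14.7 | 0.036 |
| 4 in SEL-212 only | 17.3 | 0.017 |
| 4 in each arm | 12.0 | 0.070 |
| 4 in KRYSTEXXA only | 6.7 | 0.21 |

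The direction depends entirely on which arm has more such exits.

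**The case against.** **The patient in question may be uncommon.** Protocol 8.2.1.3.1 says dosed patients should generally be followed through TP6, so a reaction normally ends drug and not participation. Protocol 5.5 says reactions on KRYSTEXXA usually follow loss of urate lowering, so many such patients would meet a stopping rule or fail TP3. This limits the numbers but does not remove the case. The per-protocol definition in SAP 5.5 itself foresees patients leaving the study after drug withdrawal for an adverse event or at investigator discretion.

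**A contrast with the primary is useful.** The primary already fails every study dropout, and crediting observed TP3 data varies that assumption in the other direction. A reason-neutral rule also avoids judging withdrawal reasons in an open-label trial. Both arguments have force. But they do not fit a purpose stated as Covid-19, and they leave pandemic loss and treatment failure mixed.

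**Other outputs would show an imbalance.** Kaplan-Meier curves and log-rank tests for study termination, including termination due to adverse events, are planned (SAP 6.1), as are single-period responder analyses (SAP 7.2.1). They would reveal the problem but do not change how this analysis scores patients.

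**Stronger readings that a reader might infer.** It is tempting to say that every dropout is scored on TP3, that such a patient is always a responder, or that the analysis can only raise results. Bullet 1 fails stopping-rule withdrawals, and it can lower a patient whose pooled time still reaches 80%. Responder status under bullet 2 needs at least 80% in TP3. Nor do the documents show that the rule favours SEL-212. They cite infusion reactions in about 26% on KRYSTEXXA (Protocol 5.5) and low incidences on SEL-212 (Protocol 7.6.3.2), which could mean that the comparator gains. They give no rates of leaving the study after TP3 in either arm.

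**Conclusion.** The point holds as a cheap improvement to a supportive analysis. Bullet 2 is wider than its stated purpose and scores a patient who leaves after TP3 more favourably than one who stays and loses control. Relative to the primary analysis it can only raise an arm's response among study withdrawals, by 1.33 points per patient. The gain of 5-8 points per arm rests on the assumed 10% leaving and 50-80% TP3 control. The size and sign of the effect on the treatment difference cannot be determined from the documents.

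A reader might infer that the trial's main conclusion is at risk. It is not: the confirmatory CMH test in the ITT set scores all study withdrawals before the end of TP6 as non-responders, and its type 1 error is unaffected.

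**What to change.** Amend bullet 2 in SAP 7.1 so that:
- TP3-only scoring applies to withdrawals documented as Covid-19-related and to patients cut short by sponsor termination of the study;
- all other study withdrawals before the end of TP6 remain non-responders, as in the primary analysis;
- bullet 1 takes precedence when a patient fits both bullets.

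The cost is one clause and one classification step. Withdrawal reasons are already recorded (Protocol 8.2.1.3.1) and tabulated (SAP 6.1). The existing Covid-19 flag covers protocol deviations and not withdrawals, so each recorded reason must be classified as Covid-19-related or not, preferably before results are seen. Indirect pandemic effects will leave some judgement calls in an open-label trial. That is the main downside.
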